#### 7.6.3 Lost to Follow-up

Principal Investigator or designee(s) must make reasonable attempts to contact participants that are lost to follow-up, in order to obtain health status and reason for withdrawal. These attempts must be documented in the study forms.

#### 7.6.4 Discontinuation of Trial

If the Investigator, the Sponsor or the Medical Monitor becomes aware of conditions or events that suggest a possible hazard to subjects if the clinical study continues, then the clinical study may be terminated after appropriate consultation among the involved parties. Also, the clinical study may be terminated at the Sponsor's discretion in the absence of such a finding. Should the study be terminated and/or the site closed for whatever reason, a copy of all documentation pertaining to the study and the study medication must be returned to the Sponsor. All site-specific documents will be archived at study site.

Approved by: [name] No.: SARO.20.001
[name]	Version No.: 4.0

### CONFIDENTIAL Page 40 of 109

#### 8. STUDY TREATMENTS/INVESTIGATIONAL PRODUCT (IP) MANAGEMENT

The participant will be instructed to take one Saroglitazar Magnesium 4 mg or Placebo tablet once daily in the morning before breakfast without food for a period of 24 weeks.

#### 8.1 TREATMENTS TO BE COMPARED

#### 8.1.1 Investigational Product Description

Source: Investigator's Brochure[26]

The IPs that will be used in this study are outlined in Table 3.

**Table 3: Identity of Study Drugs** 

Study Drug	Formulation Formulation	Strength	Route	Manufacturer
Saroglitazar Magnesium	Tablet	4 mg	Oral	
Placebo	Tablet	Matching Placebo	Oral	

Approved by: Dr.

[figure not shown]
[name]

Protocol No.: SARO.20.001

Version No.: 4.0

#### CONFIDENTIAL Page 41 of 109

#### **8.1.2** Comparator Drug Description

Placebo will be used as comparator, which will be formulated as identical appearing tablets, and will contain all the excipients mentioned in Table 4, except Saroglitazar Magnesium. The IP will be manufactured following pharmaceutical grade cGMP guidelines.

#### 8.2 DOSAGE AND TREATMENT SCHEDULE

Participants will ingest either Saroglitazar Magnesium 4 mg or Placebo orally once each morning before breakfast without food for a period of 24 weeks.

However, on every scheduled clinical visit, participants will be instructed not to take the IP until after fasting blood sample collection.

#### 8.3 PACKAGING, LABELLING AND SUPPLY

The study medication will be packaged by the sponsor according to all the local legal requirements.

Approved by: [name]	Protocol No.: SARO.20.001 Version No.: 4.0	

#### CONFIDENTIAL Page 42 of 109

An adequate quantity of the study medication will be shipped to each site. The site's investigational drug pharmacy will maintain an accurate record of the receipt of the study medication, including the date received. Until dispensed to the participants, the study medication will be stored at room temperature (20°C to 25°C or 68°F to 77°F) in a dry place at the study site or pharmacy in a secure locked area and that is accessible to authorized personnel only.

#### 8.4 STORAGE CONDITIONS

Investigational products will be stored at room temperature (20°C to 25°C or 68°F to 77°F) in a dry place excursions permitted to 15-30°C (59-86°F) at the study site or pharmacy. If the IP temperature extends outside the 20°C to 25°C range, a temperature excursion must be documented in the study-specific temperature log, and sent to the sponsor. If the excursion is within 15°C to 30°C (59°F to 86°F), quarantine is not required, and the IP is acceptable for use. If the excursion is outside of the 15°C to 30°C range, the IP must be quarantined until a decision on the stability of the IP is made by the sponsor. If the excursion goes beyond the range of 15°C to 30°C, it will be considered as a protocol deviation. All IP supplies in the study will be stored at the study site or pharmacy in a secure locked area that is accessible to authorized personnel only. Participants should store the study medication at 25°C (77°F) with excursions permitted to 15 to 30°C (59 to 86°F) [see USP Controlled Room Temperature]. Keep container tightly closed.

#### 8.5 BLINDING/UNBLINDING

The study will be performed in a double-blind manner. All study medication will be supplied in identical packages and study medication bottles. The study medication tablets will be similar in color, smell, taste, and appearance, thereby maintaining double-blind conditions.

The intent of blinding is to limit the occurrence of conscious and unconscious bias in the conduct and interpretation of the clinical study. The essential aim of blinding, therefore, is to prevent identification of the treatments by the investigator, participant, and others associated with the conduct of the study until all such opportunities for bias have passed.

All members of the clinical study team, investigators, and site staff will be blinded to treatment assignments while the study is in progress. In addition, biostatisticians who are directly involved in the analysis of the study results will remain blinded to treatment assignment while the study is in progress. For the purposes of Data and Safety Monitoring Board (DSMB) review, a separate unblinded statistician will be utilized; further details will be included in the DSMB Charter.

In case a participant experiences an AE, which meets the criteria of a Suspected Unexpected Serious Adverse Reaction (SUSAR) in order to fulfill expedited regulatory reporting requirements

Approved by: [name] No.: SARO.20.001
[name]	Version No.: 4.0

#### CONFIDENTIAL Page 43 of 109

or in the event of a medical emergency during the study where the knowledge of participant treatment is required, the investigator will unblind the treatment assignment for a specific participant via IWRS. In this event, neither the Sponsor representatives nor any other study personnel will have access to the treatment code. This level of blinding will be maintained throughout the conduct of the study. The Investigator should notify the Sponsor prior to unblinding a participant if there is sufficient time. Further, the Sponsor must be informed whenever the randomization code is broken and the reasons for unblinding.

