#### 12.2.2 Emergency Code Break (Unblinding)

An emergency code break will be available to the Investigator and/or pharmacist. This code break must only be opened in emergency situations when the identity of the study medication must be known by the Investigator in order to provide appropriate medical treatment. If the code break for a participant is opened, Sponsor must be informed immediately. The reason for opening the code break must be documented along with the date and the initials of the person who broke the code. Participants whose treatment assignment becomes unblinded inadvertently, need not require to complete the scheduled evaluations and the participant will be withdrawn from the trial from that visit.

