#### 12.4.2.1 Reporting Serious Adverse Events

The investigator must report any SAEs to the Sponsor/Service provider within 24 hours of becoming aware of the event.

During SAE reporting, the reporting SAE, the investigator's name, participants name and the telephone number with the protocol number and title will be recorded. Details regarding the safety management will be specified in safety management plan.

The investigator and the sponsor (or sponsor's designated personnel) will review each SAE report and the sponsor will evaluate the seriousness and the causal relationship of the event to the study medication. In addition, the sponsor (or sponsor's designated personnel) will evaluate the expectedness according to the reference document (Investigator Brochure or Summary of Product Characteristics).

Based on the investigator and sponsor's assessment of the event, a decision will be made concerning the need for further action. All SAEs will be recorded from first dose of study medication until the end of the study (i.e., the safety follow-up). Information regarding SAEs will be transmitted to the sponsor using the SAE Form, which must be completed and signed by a member of the investigational staff, and transmitted to the sponsor within 24 hours.

The study sponsor or designee will be responsible for notifying the FDA of any unexpected fatal or life-threatening suspected adverse reaction as soon as possible, but in no case later than 7 calendar days after the sponsor's initial receipt of the information. In addition, the sponsor must notify FDA and all participating investigators in an Investigational New Drug (IND) safety report of potential serious risks, from clinical trials or any other source, as soon as possible, but in no case later than 15 calendar days after the sponsor determines that the information qualifies for

Approved by: [name] No.: SARO.20.001
[name]	Version No.: 4.0

#### CONFIDENTIAL Page 82 of 109

reporting. If the FDA determines that a change to the investigator's brochure, IND, or protocol is needed, the Sponsor will send a copy of the IND Safety Report to the IRB, and all clinical centers, with instructions to forward the report to their local IRB.

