#### 12.4.4 Expected Adverse Events

No Suspected Adverse Reactions are considered expected by the sponsor for the purpose of expedited reporting of Suspected Unexpected Serious Adverse Reactions. .

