If necessary, the Sponsor may be required to unblind a subject if an adverse event (AE) meets criteria of a Suspected Unexpected Serious Adverse Reaction (SUSAR) in order to fulfil expedited regulatory reporting requirements. In this event, the Sponsor Medical Expert will not divulge the treatment code to

any other personnel involved in reporting, obtaining, and/or reviewing the clinical evaluations. This level of blinding will be maintained throughout the conduct of the study.

In the event of a medical emergency during the study where the knowledge of subject treatment is required, an individual Principal Investigator will have the ability to unmask the treatment assignment for a specific subject. The Investigator should notify the Sponsor prior to unmasking a subject if there is sufficient time. Further, the Sponsor must be informed whenever the randomization code is broken. The reason for unblinding should be clearly and fully documented by the Investigator.

Once all study data have been verified, validated, and the database is locked, individual subjects will be unmasked to their treatment.

During this study, no unblinding done due to any safety reason.

[figure not shown]
[figure not shown]
SAFETY DATA PLAN

FOR

SARO.20.001

CONFIDENTIAL

PAGE 7 OF 12

[figure not shown]
SAFETY DATA PLAN

FOR

SARO.20.001

CONFIDENTIAL

PAGE 8 OF 12

4 Protocol Deviations/ Violations/ Changes from Protocol:

Protocol deviation will be included in CSR.

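### Protocol 8.5 has the investigator break the code for SUSAR reporting and withholds it from the sponsor who files the report, in conflict with 12.4.2.1 and the SAP

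*Protocol*

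**What the plan says.** Protocol 8.5 (Blinding/Unblinding) names two triggers in a single sentence. The first is an adverse event that qualifies as a "Suspected Unexpected Serious Adverse Reaction (SUSAR) in order to fulfill expedited regulatory reporting requirements". The second is a medical emergency in which the treatment must be known. For both, "the investigator will unblind the treatment assignment for a specific participant via IWRS", and "neither the Sponsor representatives nor any other study personnel will have access to the treatment code". What the sponsor receives is notice: "the Sponsor must be informed whenever the randomization code is broken and the reasons for unblinding". The same section says that blinding is meant to stop the investigator, among others, from identifying the treatment, and that investigators and site staff stay blinded while the study runs.

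Protocol 12.2.2 (Emergency Code Break) provides a code break for the investigator or pharmacist and limits it: "This code break must only be opened in emergency situations", where the treatment must be known in order to treat.

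Protocol 12.4.2.1 places regulatory reporting elsewhere: "The study sponsor or designee will be responsible for notifying the FDA of any unexpected fatal or life-threatening suspected adverse reaction". It also has the sponsor evaluate seriousness, causal relationship and expectedness. Protocol 12.4.4 adds that "No Suspected Adverse Reactions are considered expected by the sponsor" for expedited reporting.

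The SAP (section 2, Blinding and Un-blinding) treats the triggers separately. For a SUSAR, "the Sponsor may be required to unblind a subject if an adverse event (AE) meets criteria of a Suspected Unexpected Serious Adverse Reaction", and the Sponsor Medical Expert keeps the code from other personnel involved in the clinical evaluations. For a medical emergency, the Principal Investigator may unmask the subject.

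**The concern.** The reason that 8.5 gives for breaking the code on a SUSAR is regulatory. The person told to break it has no regulatory filing to make, and the party that files is shut out. Nothing in the SUSAR half of the rule depends on how the participant is to be treated.

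The investigator assesses severity and causality for every adverse event (12.4.1.4, 12.4.1.5), may modify permitted concomitant medication (8.8.2), and looks after the other participants at the site. Safety and tolerability is a stated objective. Knowing one participant's arm without needing it can colour later ratings for that participant and the investigator's expectations about others. A site that reads 8.5 beside 12.2.2 is also left unsure whether a code break for reporting is permitted.

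**Working it through.** No figure in the plan bears on this point, so the check compares the texts.

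| Question | Protocol 8.5 | Protocol elsewhere | SAP section 2 |
|---|---|---|---|
| Who breaks the code for a SUSAR? | Investigator, via IWRS | 12.2.2 provides only for emergencies | Sponsor |
| Who holds the code afterwards? | Investigator; sponsor representatives and other study personnel excluded | Not addressed | Sponsor Medical Expert, who does not pass it on |
| Who reports to the FDA? | Not stated | Sponsor or designee (12.4.2.1) | Not stated |
| Who decides that the event is unexpected? | Not stated | Sponsor (12.4.2.1); none treated as expected (12.4.4) | Not stated |
| Who unmasks in a medical emergency? | Investigator | Investigator or pharmacist (12.2.2) | Principal Investigator |

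1. *Medical emergency.* All three texts give the investigator the code. There is no conflict here.

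2. *SUSAR, who breaks the code.* 8.5 says the investigator; the SAP says the sponsor. This is a direct conflict.

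3. *SUSAR, who needs the code.* 8.5 justifies unblinding by expedited reporting. 12.4.2.1 gives that reporting to the sponsor or designee. The code therefore goes to a party that does not report, while the reporting party gets only notice of the break and its reasons.

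4. *SUSAR, who recognises it.* The sponsor evaluates expectedness under 12.4.2.1, so the investigator must act on a classification that the sponsor completes.

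5. *Consistency with the stated aim.* 8.5 says that blinding should keep the investigator from identifying the treatment. Its SUSAR clause sets that aside with no treatment need.

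6. *Reach.* If no suspected reaction is expected (12.4.4), seriousness and suspected causality are enough to make an event a SUSAR. Any serious suspected reaction could then trigger investigator unblinding. I say could, because 12.4.2.1 also has the sponsor judge expectedness against a reference document that is not in the file.

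7. *Which data are exposed.* Baseline and Week 24 MRI-PDFF for the primary endpoint are read centrally (10.1). Possible drug-induced liver injury is adjudicated by a blinded committee (12.4.3). What remains exposed is later adverse event assessment by the unblinded investigator, and participant management at that site.

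8. *Occurrence.* The SAP reports four randomized subjects, no primary efficacy data, and no unblinding for safety reasons. The count of affected participants in this trial is zero.

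**The case against.** The strongest defence is the precedence clause in Protocol 11.1, under which the SAP prevails where the two differ; the SAP separates the triggers sensibly. This carries limited weight. The clause sits in the statistical section and concerns analysis definitions and methods. The SAP is a safety data plan written after the sponsor had terminated the study, so it could not have guided sites, which act on the protocol.

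Other parts of the defence stand, and they rule out stronger readings that a reader might infer.

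- *That 12.2.2 flatly contradicts 8.5.* Its limit can be read as applying only to the emergency code break named in its heading, not to IWRS unblinding under 8.5. The two sit poorly together, and the wording allows no firmer statement.
- *That the sponsor cannot meet its reporting duty.* 12.4.2.1 does not say that the notification must contain the treatment code. The documents show that unblinding under 8.5 does not serve its stated purpose; they do not show that reporting becomes impossible.
- *That the bias can be sized from the design.* An average of 120/8 = 15 participants per centre says nothing about how many SUSARs would arise or how ratings would shift. Randomization is blocked within centre (8.6), but without a block size one cannot say how far one revealed code narrows the guess for others.
- *That the triggering event's own causality rating is compromised.* An event must already be suspected to be drug-related before it is a SUSAR, so that first rating normally precedes the break. Section 7.6.1.1 also stops study drug for many such events, which limits later on-treatment exposure.

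The merged sentence may well be a drafting slip and not a deliberate design choice. That affects how it is described, not whether it needs correcting.

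**Conclusion.** The inconsistency is real and stands in the current text. For a SUSAR, Protocol 8.5 disagrees with 12.4.2.1 on who needs the code, with the SAP on who breaks and holds it, and with its own statement of why the study is blinded. It is awkward beside 12.2.2.

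Its scope is limited. It applies to SUSARs and not to emergencies. The possible bias lies in later safety assessment and participant management; the central MRI-PDFF reading is not touched. No magnitude can be given, because no SUSAR rate is stated and none can be derived from the documents. In this trial nothing followed from it.

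The conclusion rests on two readings: that the denial of access in 8.5 covers both triggers, as the sentence order indicates, and that 12.4.4 means what it says about expectedness. If the denial were confined to emergencies, the investigator would still be the one told to break the code for a SUSAR, and the conflict with the SAP would remain. The correction should be made because it is cheap and the clause could be carried into a later protocol.

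**What to change.** Split the two triggers in Protocol 8.5, in line with the SAP.

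- *SUSAR:* a designated sponsor safety role obtains the code and discloses it to nobody who reports, collects or reviews clinical evaluations. The investigator, the site and the analysis team stay blinded.
- *Medical emergency:* the investigator's code break is kept, and 8.5 and 12.2.2 are worded so that they plainly describe the same provision.

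One element goes beyond the SAP. The SAP names the Sponsor Medical Expert, does not say that this role stands outside the study team, and does not mention IWRS for this purpose. Protocol 8.8.2 involves the Medical Expert/Medical monitor in agreeing NAFLD- or NASH-directed medication during the study. The role that receives SUSAR codes should therefore be one that takes no part in study decisions.

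Then reconcile 8.5, 12.2.2, 12.4.2.1 and the SAP so that each gives the same answer on who breaks the code, who receives it and who stays blinded. The cost is protocol wording and an IWRS role setting; sample size and analysis are unaffected.

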#### 8.6 METHOD OF ASSIGNING PARTICIPANT TO TREATMENT GROUP

Participants will be randomized in a 1:1 ratio to receive Saroglitazar Magnesium 4 mg once daily orally or Placebo. The randomization scheme will be stratified by clinical center. This scheme will ensure that the two groups will be balanced by calendar time of enrollment (to minimize secular effects) and by clinic (to minimize clinic-specific effects of differences in patient populations and management).

The randomization scheme will be prepared by an unblinded statistician or designee. Requests for randomizations will be made by the clinics using IWRS (Interactive Web Response System). An assignment will be issued only if the database shows that the patient is eligible, has signed the consent statement, and has had all required baseline data keyed into the database.

Treatment assignments are double masked throughout the study until all data collection for the trial has been completed (i.e., after completion of the post-trial follow-up for all participants). The block randomization schedule will be generated using SAS® software (Version: 9.4 or higher; SAS Institute Inc., USA).

#### 8.7 SELECTION OF DOSES

Saroglitazar Magnesium 4 mg has been selected for this study based on previous pharmacokinetics, dose ranging studies, HIV lipodystrophy study, and two published studies in primary NAFLD.

### 8.8 CONCOMITANT MEDICATIONS AND OTHER RESTRICTIONS

#### **8.8.1** Previous and Concomitant Medications

Any medication the participant takes, other than the study drug, including herbal and other non-traditional remedies, is considered a concomitant medication. All concomitant medications and any changes in the dosage or regimen of a concomitant medication for the 6 months preceding Visit 1 (screening visit) until the end of the study (i.e., the safety follow-up visit-12) must be recorded in the CRF.

Approved by: [name] No.: SARO.20.001
[name]	Version No.: 4.0

#### CONFIDENTIAL Page 44 of 109

#### **8.8.2** Permitted Concomitant Medication:

- With the exception of prohibited concomitant medications, the following medications that the participants have been taking at stable dosages for at least 3 months before screening (Visit 1) until the end of study will be permitted as concomitant medications:
- o Lipid-lowering drugs- statins and fibrates,
- o Anti-hypertensives
- o Stable ART regimen.
- The SGLT2 inhibitors (e.g. canagliflozin, empagliflozin, dapagliflozin, etc.), glucose-dependent insulinotropic polypeptide (GIP) and/or GLP-1 agonists (e.g. semaglutide, exenatide, liraglutide, lixisenatide, tirzepatide etc.) that the participants have been taking stable doses for at least 6 months before screening (Visit 1) until the end of study
- Antidiabetic medications i.e., metformin, sulfonylureas, insulin, dipeptidyl peptidase 4 inhibitors (gliptins) will be permitted if the dose has been stable for 3 months prior to screening (visit 1) until the end of study
- In case of further adjustment of anti-diabetic treatment is needed during the study, the following guidance should be exercised in line with local standard practice as considered appropriate by treating physician:
  - Maximizing doses of metformin, dipeptidyl peptidase 4 inhibitors (DPP-4 inhibitors or gliptins), sulfonylurea (excluding those more prone to induce hypoglycemia).
  - For participants receiving SGLT2 inhibitors, GIP and/or GLP1-RAs at screening, it is recommended to avoid increase in dose of SGLT2 inhibitors, GIP and/or GLP1 RAs throughout study.
  - o For participants not receiving SGLT2 inhibitors, GIP and/or GLP1-RAs at screening, treatment with SGLT2 inhibitors, GIP and/or GLP1-RAs should not be started throughout study.
- The Investigator at his/her discretion will also be allowed to offer a rescue medication for clinically significant conditions correlated with the laboratory findings, if required, however, such interventions shall be recorded in the eCRF with description of type of intervention, dose and duration. Throughout the study, investigators may prescribe any concomitant medications or treatments deemed necessary to provide adequate supportive care except for prohibited medications listed in Section 8.8.3. If medication given is in violation to the protocol, then such subjects will be withdrawn from the trial. Allowed overthe-counter medications (OTC) such as acetaminophen (maximum 1 gram/day), ibuprofen (maximum 800 mg/day), naproxen (maximum 440 mg/day), antacids such as H2 receptor blockers, and proton-pump inhibitors for shorter duration (up to 14 days) as per the investigator's discretion. Participants will also be instructed about the importance of not

Approved by: [name] No.: SARO.20.001
[name]	Version No.: 4.0

#### CONFIDENTIAL Page 45 of 109

taking any other medication throughout the study (including OTC medications) without consulting the Investigator.

- The stable doses of allowed concomitant medications should not be changed either at/between the screening visits or at randomization visit. Upon randomization of participants, they will be discouraged from making any changes in allowed concomitant medications and encouraged to make alternative options. However, the site investigator at his/her discretion can modify the dose of the current regimen or change any permitted medication to another permitted medication if clinically indicated.
- The site investigator should be alerted if, during the course of the study, a participant requires a new medicine or therapy or a change to an established dosing regimen. All medications that target NAFLD or NASH, or have been suggested to target the underlying causes of NAFLD or NASH, should be reviewed and agreed upon by the Investigator and Sponsor's representatives including Medical Expert/Medical monitor before being taken by the participant.

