#### 10.2.5 Early Termination (ET) visit

Participants prematurely discontinued from the study would be encouraged to complete an ET visit within 30 days of last dose. The investigator should make every effort to perform following assessments at the early termination visit in case if any participant discontinues from

Approved by: [name] No.: SARO.20.001
[name]	Version No.: 4.0

#### CONFIDENTIAL Page 60 of 109

the study prior to completion of his/her study treatment period (i.e. termination prior to Week 24 visit):

- Complete physical examination
- Vital signs measurement.
- AE assessment.
- Concomitant medication review
- Monitoring of diet, exercise, avoidance of alcohol, and other hepatotoxic agents (Refer Appendix 8).
- Compliance review for study medication
- Weight, Hip and waist minimal circumference measurements
- Fasting Laboratory evaluations
- Serum pregnancy test for all female participants of child bearing potential.

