#### 11.5 PRIMARY EFFICACY ANALYSIS

#### 11.5.1 Intercurrent Events

The following intercurrent events (ICEs) are envisioned during the study:

- Death
- Premature discontinuation of study treatment for reason other than AE, lack of efficacy (LoE), liver transplant, hepatic decompensation or bariatric intervention.
- Premature discontinuation of study treatment for reason of AE, lack of efficacy (LoE), liver transplant, hepatic decompensation or bariatric intervention.
- Receipt of prohibited medication at any point prior to Week 24 assessment.

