#### 11.5.2.2 Definitions Corresponding to Each Estimand

	Primary Estimand	Secondary Estimand	
ICEs and strategies to handle ICEs	Death prior to assessment at Week 24     Composite strategy     Premature discontinuation of study treatment for reason of AE, lack of efficacy (LoE), liver transplant, hepatic decompensation or bariatric intervention     Treatment policy strategy     Premature discontinuation of study treatment for reason other than AE, lack of efficacy (LoE), liver transplant, hepatic	Death prior to assessment at Week 24     Composite strategy     Premature discontinuation of study treatment for reason of AE, lack of efficacy (LoE), liver transplant, hepatic decompensation or bariatric intervention     Hypothetical strategy     Premature discontinuation of study treatment for reason other than AE, lack of efficacy (LoE), liver transplant, hepatic	
	decompensation or bariatric intervention  Treatment policy strategy	decompensation or bariatric intervention  Hypothetical strategy	
	Receipt of prohibited medication at any point up to Week 24  Treatment policy strategy	Receipt of prohibited medication at any point up to Week 24  Hypothetical strategy	
	ICE(s) with a composite variable strategy take priority over ICEs with other strategies.		

Where the strategies are described as follows in the sequence these strategies will be applied:

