#### • For the primary estimand:

- Composite strategy: missing data will be handled by imputing using the worst outcome of MRI-PDFF across either treatment arm.
  - o Treatment policy strategy: available data occurring on or after the ICE will be analyzed as observed. Any missing Week 24 MRI-PDFF data due to discontinuation of study treatment for reason other than AE, lack of efficacy (LoE), liver transplant, hepatic decompensation or bariatric intervention will be multiple imputed using a missing at random (MAR) approach.
- For the secondary estimand:
- Composite variable strategy: missing data will be handled by imputing using the worst outcome of MRI PDFF across either treatment arm.

Approved by: [name] No.: SARO.20.001
[name]	Version No.: 4.0

#### CONFIDENTIAL Page 65 of 109

O Hypothetical strategy: the approach allows for the assessment of the treatment effect in an alternative, hypothetical setting where 1) all participants take the assigned study treatment without discontinuation/interruption, and 2) prohibited medication was not available to participants for the study duration. Available data occurring on or after the ICE will be set to missing, and multiple imputed by a MNAR application of SAS Proc MI based on the distribution of data for each treatment arm where all participants do not experience an ICE.

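### Treatment policy for prohibited medication needs a Week 24 MRI-PDFF that the withdrawal rule in Protocol 8.8.2 may prevent (minor, wording only)

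*Protocol*

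**What the plan says.** **Estimand.** Protocol 11.5.1 names this intercurrent event: "Receipt of prohibited medication at any point prior to Week 24 assessment". The table in 11.5.2.2 lists "Receipt of prohibited medication at any point up to Week 24" under treatment policy for the primary estimand and under the hypothetical strategy for the secondary. Under treatment policy, "available data occurring on or after the ICE will be analyzed as observed". Under the hypothetical strategy, "Available data occurring on or after the ICE will be set to missing", and values are then imputed by arm from participants without an intercurrent event.

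**Imputation.** The missing-at-random (MAR) rule attached to treatment policy is worded for "Any missing Week 24 MRI-PDFF data due to discontinuation of study treatment for reason other than AE", lack of efficacy and the other listed causes. It does not name prohibited medication or withdrawal from the trial. Section 11.5.6 makes multiple imputation the general method.

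**Conduct.** In 8.8.2 investigators may prescribe treatment "deemed necessary to provide adequate supportive care except for prohibited medications listed in" Section 8.8.3. The next sentence reads: "If medication given is in violation to the protocol, then such subjects will be withdrawn from the trial". Section 10.4 leaves withdrawal after a serious deviation to the sponsor or the investigator. Section 7.6.2 lists non-compliance, including major deviations, as a ground for discontinuation from the study.

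**Data collection.** Section 10.2.5 says: "Participants prematurely discontinued from the study would be encouraged to complete an ET visit within 30 days of last dose". Its list of assessments has no MRI-PDFF. The visit lists in 10.2 give MRI-PDFF at Visit 1 and at Visit 9 (Week 24/EOT) only. Section 7.4 offers continued follow-up to those who want to stop study medication, and safety follow-up within 4 weeks to treated participants who do not complete. Section 11.5.6 commits to trying to prevent early termination and to going on collecting data after study drug is stopped.

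**The concern.** Treatment policy is informative only if the outcome is measured after the event. The protocol names the event, chooses to use the data that follow it, and in another section removes the participant from the trial. There is a single post-baseline scan, so a participant withdrawn before Visit 9 has no earlier on-treatment MRI-PDFF to inform imputation. The imputed value would rest on baseline and on other participants in the arm, nearly all without this event. That is close to what the secondary estimand does by design. Section 11.5.2.2 deliberately separates the two estimands for this event, and that separation would be partly lost.

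**Working it through.** **1. The plan's own figure.** Inputs from Protocol 11.11: difference 3, SD 6, one-sided 5%, power 80%, dropout 15%. The exact one-sided t calculation gives 51 per arm (power 80.6%; 50 per arm gives 79.9%), so 102 evaluable. 102/0.85 = 120. The stated 102 and 120 reproduce.

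**2. Who would lack the scan.**

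| Rule applied | Event found before Visit 9 | Event found at Visit 9 |
|---|---|---|
| 8.8.2 as written | No Week 24 scan, unless 11.5.6 is read to apply | Scan may still be done |
| 10.4 discretion | Share unknown | Scan may still be done |

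Visit 8 is at Day 113 and Visit 9 at Day 169, with no visit between: 169 - 113 = 56 days. If onset is uniform over 168 days of treatment and events are found at scheduled visits (both assumed), the share found at Visit 9 is u = 56/168 = 1/3.

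**3. Size of the error.** The documents give no event rate and no effect of the event on liver fat. Assumed: a fraction r = 1% to 5% of the active arm only (0.6 to 3 of 60), a shift s = +3 or -3 points after the event (+ means more liver fat), and imputation that reproduces participants without the event.

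- Treatment-policy effect: 3 - r·s
- Estimate when only the share u is scanned: 3 - r·u·s
- Error: r·s·(1 - u)

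| r | s | True effect | Estimate, u = 0 | Error | Estimate, u = 1/3 | Error |
|---|---|---|---|---|---|---|
| 1% | +3 | 2.97 | 3.00 | +0.03 (+1.0%) | 2.99 | +0.02 (+0.7%) |
| 5% | +3 | 2.85 | 3.00 | +0.15 (+5.3%) | 2.95 | +0.10 (+3.5%) |
| 1% | -3 | 3.03 | 3.00 | -0.03 (-1.0%) | 3.01 | -0.02 (-0.7%) |
| 5% | -3 | 3.15 | 3.00 | -0.15 (-4.8%) | 3.05 | -0.10 (-3.2%) |

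If the events fall in the placebo arm instead, the signs reverse. Equal rates and shifts in both arms cancel. A simulation (40,000 trials, 60 per arm, r = 5% in the active arm) agrees: for s = +3, full scanning gives 2.853, against 3.003 with no scans; with one third scanned the pair is 2.851 and 2.950.

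**4. Against the planned precision.** SE = 6 × √(2/n): 1.188 at 51 per arm and 1.095 at 60 per arm. So 0.15 is 0.126 to 0.137 SE, and 0.10 is 0.084 to 0.091 SE.

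**5. Power.** At 5% of an arm, 0.05 × 60 = 3 scans are lost. The plan allows 0.15 × 60 = 9. If the 3 fall within the 9, planned power is unchanged. If they come on top, 60 × 0.80 = 48 per arm remain and power is 78.4%.

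**The case against.** A reader might infer that most participants with this event would have no Week 24 scan, so that treatment policy could not be carried out. The documents do not support so firm a statement.

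- It follows from 8.8.2 alone. Under the discretion in 10.4 the share is unknown. The 8.8.2 sentence speaks of medication given, directly after a sentence on prescribing. The intercurrent event is any receipt, so it is unclear whether 8.8.2 reaches products that participants take on their own.
- A participant withdrawn from the trial also stops study drug, and so arguably falls under the promise in 11.5.6 to keep collecting data. The same section promises efforts against early termination.
- Section 10.6 says results will be analysed for all participants whatever their deviations. However, it also lists leaving in a participant who met the withdrawal criteria as a deviation, which discourages a site from keeping such a participant for the scan.
- The Section 2 schedule is not in the text available here, so an early-termination MRI cannot be excluded. Even so, an early scan would not be a Week 24 value.

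A reader might also infer a material or one-directional bias. Section 8.8.3 prohibits both drugs with potential effects on NAFLD and drugs that cause steatosis, so the direction is open. It also prohibits CYP2C8 inhibitors and substrates, for which the documents give no reason to expect a 3-point shift. Putting every event in one arm of a double-blind trial, with a shift equal to the whole planned effect, is a severe assumption.

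These objections lower the severity and rule out the word most. They do not remove the conflict: 8.8.2 is mandatory, 10.4 is discretionary, and neither says whether the scan is still wanted. Missing data are largely provided for by 11.5.6 and the MAR rule, so naming the rule for this event is a clarification rather than a repair.

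**Conclusion.** The inconsistency is real and minor. Followed as written, 8.8.2 removes the observation that the primary estimand relies on when the event is found before Visit 9, subject to how 11.5.6 is read. To that extent the primary estimand moves towards the secondary for this event. Under the assumptions above the error is at most about 0.15 points (0.14 SE), and about 0.10 points if one third of events surface at Visit 9. Planned power holds if the losses fall within the 15% dropout.

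No reported result is affected. The SAP introduction says the trial was terminated, four participants were randomized and no primary endpoint data were collected. The point matters for the design record and for any reuse of this protocol.

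**What to change.** Reconcile Protocol 7.6.2, 8.8.2, 10.2.5, 10.4, 11.5.2.2 and 11.5.6. Which withdrawal rule should stand is for the sponsor to decide, and this review takes no position on it.

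Whatever is decided, state that a participant who has this event and has not withdrawn consent is still asked to attend the already scheduled Week 24 MRI-PDFF for data collection. The text should make clear that withdrawal under 8.8.2 does not in itself end that request.

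Optional clarification: confirm in 11.5.2.2 that the existing MAR rule covers a scan still missing after this event.

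Cost: wording only, since the Week 24 scan is already planned for everyone. If 1-5% of both arms had the event, sites would need to bring back about 1 to 6 of 120 participants (0.01 × 120 = 1.2; 0.05 × 120 = 6).
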